3.0 BACKGROUND AND STUDY RATIONALE

3.1. Background

The incidence of malignant melanoma continues to increase globally, and this includes Asia. Up to the end of 2010, the incidence of melanoma in Beijing, China was 8.9 per 100000 people (Si 2013). Melanomas can be generally classified into 4 subtypes: (1) melanomas that occur on skin without chronic sun-induced damage (non-CSD); (2) melanomas on skin with chronic sun-induced damage (CSD); (3) mucosal melanomas, and (4) acral melanomas. The incidence of these 4 subtypes differs significantly among different races and ethnicities (Kong 2011). In the Chinese and other Asian populations, acral and mucosal melanomas are the predominant subtypes, accounting for approximately 65% of all melanomas (Chi 2011). Five-year survival rates of Chinese patients with stage I, II, III, and IV diseases were 94.1%, 44.0%, 38.4%, and 4.6%, respectively (Chi 2011).

In a large analysis which comprised 502 samples from melanoma patients screened for KIT mutations at Peking Cancer Hospital & Institute, the overall mutation frequency was 10.8% (54/502), with the highest mutation frequency within the CSD subgroup (20.7%); in the acral and mucosal melanoma subtypes, the frequency of KIT mutations was 11.9% (23/193) and 9.6% (16/167), respectively. Importantly, the overall survival of melanoma patients with KIT mutations was significantly shorter than that of patients without such alterations ($p = 0.001$) (Kong 2011).

Until recently, there had been no improvements in outcome for patients with advanced disease for several decades. The identification of an activating mutation in BRAF in 50% of melanoma patients (Davies 2002) led to the development of vemurafenib, a highly active targeted therapy that benefits approximately 80% of eligible patients, is associated with a significant survival benefit, and is now a standard of care in advanced disease (Chapman 2011). Apart from BRAF, KIT is the only other aberrant signaling molecule for which targeted drugs are available. Some evidence of efficacy for imatinib in KIT advanced melanoma has been reported in two Phase II trials (Guo 2011). However, KIT mutations are heterogeneous, and many do not respond to imatinib therapy (Si 2013; Carvajal 2011). To date, there has been no therapy approved for KIT mutated melanoma.

PLX3397 is a novel, orally active, small molecule inhibitor that targets a variety of KIT mutations, as well as CSF1R (Fms), and oncogenic Flt3, but remains highly selective versus other kinases. Few preclinical models for Kit-mutant melanoma exist, but preliminary results from an ongoing study of PLX3397 in one model are promising. This model is based on a patient-derived tumor xenograft from a patient with sinal-nasal melanoma. This patient had been treated with the kinase inhibitor nilotinib and experienced partial tumor regression at 3 months. After 6 months a new subcutaneous lesion appeared and a biopsy of this lesion was removed and propagated in immunocompromised mice. Tumors in these mice grew to 100 mm³ in 12 days and treatment with PLX3397 (chow formulation, nominal strength of 46 mg/kg) was initiated. As shown in Figure 3-1 below, vehicle-treated animals ($n = 12$) were sacrificed at Week 7, while PLX3397 treatment resulted in tumor regression ($n = 12$). PLX3397 treatment was stopped at Week 13, and three of the 12 animals showed re-growth of the tumor.

[figure not shown]

Figure 3-1: PLX3397 Causes Tumor Regression in a Patient-Derived Xenograft Model of Kit-Mutant Melanoma

It is now widely accepted that tumor-associated macrophages (TAMs) play a critical role in promoting tumor angiogenesis, metastasis and creating an immunosuppressive microenvironment for tumor growth (Hao 2012). PLX3397 targets these TAMs by blocking the Fms receptor on their surface. Pharmacology models show that PLX3397 blocks Fms activity in vivo, and significantly reduces the incidence of lymph node metastasis in the A2058 BRAF-mutant xenograft model. In addition, synergistic efficacy is demonstrated when PLX3397 is combined with BRAF inhibition in this same model, providing a possible explanation for the beneficial effect of FMS blockade in the tumor microenvironment. See the [PLX3397 Investigator’s Brochure](#) for further details.

3.1.1. Nonclinical Experience

Good Laboratory Practice (GLP) safety pharmacology studies (in vitro hERG, dog cardiovascular, rat central nervous system, and rat respiratory) did not identify any meaningful test article related effects.

In the GLP 13-week rat oral gavage study at doses of 0.5, 4 and 20 mg/kg/day, there were no test article-related clinical observations or effects on body weights, food consumption, ophthalmic examinations, urinalysis, or macroscopic examinations. Systemic toxicity was observed at a dosage level of 20 mg/kg/day, as evidenced by anemia and mild to moderate generalized bone marrow depletion in both sexes, and minimal to moderate hepatocellular vacuolation associated with higher AST, ALT, and cholesterol values in males. The no-observed-adverse-effect level (NOAEL) was considered to be 4 mg/kg/day.

In the GLP 13-week dog oral gavage study at doses of 1, 6, and 30 mg/kg/day, there were no test article-related macroscopic findings. Body weights, food consumption, ophthalmic, and electrocardiography parameters were unaffected by test article administration. Systemic toxicity was observed at the dosage level of 30 mg/kg/day, as evidenced by microscopic findings of generalized depletion of all germ cell populations in the testes, moderate hypospermatogenesis,

and moderate or severe hypospermia in the epididymides, which were consistent with observed lower absolute and relative testes weights and lower testicular volume in this group and sex. The NOAEL was considered to be 6 mg/kg/day for males.

In GLP genotoxicity studies (Ames, chromosomal aberrations, and mouse bone marrow micronucleus), there was no evidence of mutagenic or clastogenic effects.

See the [PLX3397 Investigator's Brochure](#) for further details.

3.1.2. Clinical Experience

PLX3397 is being evaluated in both solid tumors and hematological malignancies. Approximately 345 patients have been exposed to PLX3397 doses ranging from 200 mg/day to 5000 mg/day for up to 16 months. The recommended Phase II dose (RP2D) for solid tumors is 1000 mg/day, and the RP2D for patients with Flt3-ITD AML (acute myelogenous leukemia) is 3000 mg/day.

No safety signals in vital signs, physical examinations, or electrocardiograms (ECGs) (including careful evaluation of potential electrocardiogram Interval between the start of the Q wave and the end of the T wave (QT) prolongation) have been identified. At doses of ≥ 600 mg/day, transient and reversible increases in aspartate aminotransferase (AST) and/or alanine aminotransferase (ALT) have been observed in approximately half of the patients. In addition, 1 case of liver enzyme elevation in association with an elevated bilirubin which was considered possibly drug-related was noted in study PLX108-04 (Phase II, single agent study in subjects with glioblastoma multiforme). Transient increases in AST and ALT were seen in the 13-week rat study, but not in the dog study. In addition to increased AST among solid tumor patients, the most common adverse events (AEs) have been fatigue, decreased appetite, nausea, vomiting, anemia, hair color change (depigmentation), and diarrhea.

Details on the clinical experience with PLX3397 can be found in the [Investigator's Brochure](#).

3.2. Rationale for Dose Selection and Study Design

As summarized above (and discussed in detail in the [Investigator's Brochure](#)), the safety of PLX3397 has been evaluated in patients with a range of tumor types, including solid tumors, hematologic malignancy, and in combination with chemotherapeutic agents. The selection of 1000 mg per day as the initial dose to be evaluated in the Pilot portion of this study was based upon the safety data from PLX108-01, a dose-escalation study of PLX3397 in solid tumor patients followed by expansion cohorts of patients receiving PLX3397 at the RP2D. In the dose escalation portion of the study, 1000 mg per day was identified as the RP2D, and the safety of 1000 mg per day was further evaluated in over 75 additional solid tumor patients. As this is the first time PLX3397 will be studied in melanoma patients, a Pilot portion of the study will confirm the safety and tolerability of 1000 mg per day in this patient population. A dose de-escalation option will allow dose reduction to 800 mg per day in the event that 1000 mg per day is not well tolerated. Doses below 800 mg per day are anticipated to result in reduced efficacy and will not be considered in this study.

Once the RP2D is selected from the Pilot portion, the study will be expanded to include an additional 32 patients to evaluate the anti-tumor activity of PLX3397 in KIT-mutated melanoma. The Phase II portion of this study will enroll patients in two stages. Thirteen patients will be enrolled in the first stage, with at least three responses (23%) required to proceed to the second stage. With the assumption of 10% drop-out, the total sample size will be 32 patients to achieve 29 evaluable patients. Eight responses (28%) among 29 evaluable patients are required for PLX3397 to be considered promising. In view of the fact that there is no effective and approved therapy for advanced KIT mutated melanoma, a response rate of >40% is considered worthy of further study.

This study design will allow the step-wise evaluation of PLX3397 in patients with advanced KIT-mutated melanoma, with the Pilot portion evaluating the safety of the proposed RP2D of 1000 mg per day and the Phase II Portion providing for an initial evaluation of efficacy (among the first 13 enrolled patients) prior to further enrollment of the full cohort.

The Extension part of the study will allow subjects to continue pexidartinib treatment who demonstrate clinical benefit (SD, PR, or CR). The benefits of transitioning subjects into the extension part are to allow subjects to continue receiving the study drug and monitor for safety, but decrease the amount of procedures.

3.3. Potential Risks and Benefits

The safety of pexidartinib has been evaluated in subjects with a range of tumor types, including solid tumors, hematologic malignancy, and in combination with chemotherapeutic agents. The selection of 1000 mg per day as the initial dose to be evaluated in the several studies was based upon the safety data from Study PLX108-01 and the safety of 1000 mg per day was further evaluated in several clinical studies.

In the GLP repeat-dose toxicology studies consisting of up to 13 weeks of pexidartinib dosing, test article-related AEs were noted in testes (testicular spermatogonia reduction), ovaries (ovarian follicular degeneration), liver, bone and bone marrow, hematology, and lymphoid changes; these changes are consistent with the pharmacological mechanism of action of pexidartinib. All test article-related findings were partially or fully reversible. Potential dose-related changes in bone marrow function can be monitored by peripheral blood cell count and differential counts. Because of the effects on reproductive organs, subjects will be monitored for changes in luteinizing hormone, follicle stimulating hormone, and other sex-specific hormone levels.

Effects on embryo fetal development have been observed in both rat and rabbit toxicology studies. Subjects in the study will be required to use adequate birth control during the study and for 90 days after the last dose of study drug administered.

Findings in the nonclinical canine safety pharmacology study suggest that pexidartinib may have a negative inotropic effect. Subjects will be monitored for changes in ejection fraction with cardiac echocardiograms.

In the clinical evaluation to date, among solid tumor patients, the most common AEs (occurring in $\geq 20\%$ of all patients treated with pexidartinib) observed have been fatigue, nausea, decreased

appetite, hair color change (depigmentation), vomiting, diarrhea, headache, and anemia. In the AML study, the most common AEs reported have been diarrhea, nausea, fatigue, febrile neutropenia, vomiting, decreased appetite, anemia, cough, hypokalemia, and increases in AST. In some instances, the increase in liver enzymes may require dose hold or modification. Dosing modification guidance is included within the protocol for AE monitoring. Liver function (serum chemistry), renal function (serum chemistry), and heart electrophysiology (QT interval corrected for heart rate [QTc] evaluation) will be monitored during this study.

Based on the treatment emergent adverse event (TEAE) reports of increased INR observed in patients receiving concomitant warfarin, careful monitoring is required during treatment with pexidartinib. Warfarin doses should be adjusted if an increase in INR is noted.

Updated hepatic safety risk information as of December 2017; please consult the IB for more information: Hepatotoxicity is an important adverse drug reaction. Elevations of liver transaminases and bilirubin have been observed in studies with pexidartinib, together with cases of drug induced cholestasis. Cases of cholestasis have been observed in the first 8 weeks, have generally resolved with treatment discontinuation, but in some cases have been severe, with a protracted course requiring liver dialysis and, in 1 case, transplantation. Hepatotoxicity may be fatal. One fatal case with ongoing cholestatic liver injury at the time of death has been reported. Monitor patients closely as defined in the protocol. Protocol defined dose reductions and discontinuations of pexidartinib, increased frequency of laboratory monitoring, and reporting of findings should be followed (refer to Section 7.5). In addition, rechallenge with pexidartinib should not be attempted without prior discussion with the Sponsor's Medical Monitor.

Pexidartinib is a novel, orally active, small molecule inhibitor that targets CSF1R, Kit, and oncogenic Flt3, but remains highly selective versus other kinases. The potent inhibition of these 3 kinases can be exploited to attack tumors via multiple mechanisms. Pexidartinib has shown a potent inhibitor of the proliferation of these target dependent models.

4.0 STUDY OBJECTIVES

4.1. Pilot Portion Objectives

The objectives of the Pilot portion of the study are:

- To evaluate the safety profile of PLX3397 1000 mg per day when administered twice daily (BID) orally as a single agent to patients with unresectable or metastatic KIT-mutated melanoma
- To determine the pharmacokinetics of PLX3397

4.2. Phase II Objectives

The objectives of the Phase II portion of the study are:

- To determine the preliminary efficacy of PLX3397
- To evaluate the safety profile of PLX3397

4.3. Exploratory Objectives

The exploratory objectives are:

- To evaluate the pharmacodynamics as well as the association between KIT mutation type and response to therapy (Pilot and Phase II portions of the study)
- To evaluate tumor response by positron emission tomography (PET) scan on Day 1 of Cycle 2 compared to Baseline (Pilot portion and first 13 patients of the Phase II portion of the study).

5.0 STUDY DESIGN

5.1. Overview of Study Design

This Phase I/II, open label, multicenter study includes a dose evaluation portion (Pilot phase) in which the safety profile of PLX3397 as a single oral agent will be evaluated, followed by an expansion cohort (Phase II) in which the efficacy and safety of PLX3397 administered at the RP2D will be evaluated in patients with unresectable stage III or stage IV KIT-mutated melanoma (comprising mainly acral, mucosal or CSD forms of the disease).

The Pilot portion of the study follows a 3+3 design to determine if 1000 mg per day is an appropriate dose for the Phase II portion. Three patients are planned to be dosed initially. If 0 or

1 of 3 patients at the 1000 mg dose level cohort experience dose-limiting toxicity (DLT), 3 additional patients will be enrolled for a total of 6 patients. If ≥ 2 of 6 patients experience DLT at the 1000 mg dose, the dose will be de-escalated to 800 mg per day. If 0 or 1 of 3 patients at the 800 mg dose level cohort experiences DLT, 3 additional patients will be enrolled for a total of 6 patients. If ≥ 2 of 6 patients experience DLT at the 800 mg dose, the study will be terminated due to intolerability. Additional patients may be enrolled in a dose cohort based on safety and efficacy observations. The RP2D can be either 1000 mg per day or 800 mg per day based on discussions between the Sponsor and the investigators. The RP2D will be further evaluated in an expansion cohort during the Phase II portion of the study.

In the Phase II portion of the study, an analysis of anti-tumor response will be carried out after approximately 13 patients have been treated. If 3 or more responses (23%) are seen (complete response (CR) and partial response (PR) based upon Response Evaluation Criteria in Solid Tumors (RECIST) v1.1 or PET imaging), an additional approximately 19 patients will be enrolled and treated.

As of June 30 2018, 6 patients were enrolled in the Pilot portion of the study and received 1000 mg per day dose. Two subjects are currently ongoing. Following a preliminary safety and efficacy assessment of these 6 patients, the sponsor decided to discontinue this study. The sponsor informed the 2 remaining subjects of study discontinuation and re-consented the subjects to continue in the extension part of the study.

It is anticipated that a cut-off date will be established and that the data for the safety variables are considered to be mature. Subjects who benefit from therapy (stable disease or better) and remain on treatment without tumor progression at the time of cut-off will be allowed to continue treatment in an extension part of this study. Treatment will continue until disease progression, unacceptable toxicity, or consent withdrawal.

A graphic overview of the study design is presented in [Figure 5-1](#).

[figure not shown]

Figure 5-1: Overview of Study PLX3397

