Study Design:	
This Phase I/II, open label, multicenter study includes a dose evaluation portion (Pilot phase) in which the safety profile of PLX3397 as a single oral agent will be evaluated, followed by an expansion cohort (Phase II) in which the efficacy and safety of PLX3397 administered at the recommended Phase II dose (RP2D) will be evaluated in patients with unresectable stage III or stage IV KIT-mutated melanoma.
 
The Pilot portion of the study follows a 3+3 design to determine if 1000 mg per day is the appropriate dose for the Phase II portion. Three patients are planned to be dosed initially. If 0 or 1 of 3 patients at the 1000 mg dose level cohort experience a dose-limiting toxicity (DLT), 3 additional patients will be enrolled for a total of 6 patients. If ≥ 2 of 6 patients experience a DLT at the 1000 mg per day dose, the dose will be de-escalated to 800 mg per day. If 0 or 1 of 3 patients at the 800 mg per day dose level cohort experiences a DLT, 3 additional patients will be enrolled for a total of 6 patients. If ≥ 2 of 6 patients experience a DLT at the 800 mg dose, the study will be terminated due to intolerability. Additional patients may be enrolled in a dose cohort based on safety and efficacy observations. The RP2D can be either 1000 mg per day or 800 mg per day based on discussions between the Sponsor and the investigators. The RP2D will be further evaluated in an expansion cohort during the Phase II portion of the study.
 
In the Phase II portion of the study, an analysis of anti-tumor response will be carried out after approximately 13 patients have been treated. If 3 or more responses are seen (complete response (CR) and partial response (PR) based upon Response Evaluation Criteria in Solid Tumors (RECIST) v1.1 or PET imaging), an additional approximately 19 patients will be enrolled and treated.

Number of Patients:	
Approximately 44 patients are planned for enrollment
 
Pilot: Approximately 6-12 patients
 
Phase II: Approximately 32 patients

Study Procedures:	Procedures include medical history, physical examination, vital sign assessment, 12-lead electrocardiography (ECG), clinical laboratory evaluations (serum chemistry, hematology, urinalysis), pregnancy testing, and eastern cooperative oncology group (ECOG)

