11.0 STATISTICAL AND QUANTITATIVE ANALYSES

11.1. Determination of Sample Size

The Pilot portion of this study will determine if 1000 mg PLX3397 is an appropriate dose for the Phase II portion of the study. Traditional 3+3 design will be utilized to determine RP2D.

Eligible patients will enter the study in sets of three. Dose-limiting toxicity (DLT) is defined in Section 7.4. If 0 or 1 of 3 patients at the 1000 mg dose level cohort experience DLT, 3 additional patients will be enrolled for a total of 6 patients. If ≥ 2 of 6 patients experience DLT at the 1000 mg dose, the dose will be de-escalated to 800 mg per day. If 0 or 1 of 3 patients at the 800 mg dose level cohort experiences DLT, 3 additional patients will be enrolled for a total of 6 patients. If ≥ 2 of 6 patients experience DLT at the 800 mg dose, the study will be terminated due to intolerability. Each cohort of patients will be observed for toxicity for 28 days in order to allow time to identify all acute effects of PLX3397. Between 6 and 12 patients will be accrued for the Pilot portion of this study.

The primary objective of the Phase II portion of this study is to evaluate the objective response rate (ORR) at the RP2D. The RP2D will be either the MTD or the alternate dose level below the MTD determined by sponsor and investigator. A true response rate of 40% or more will be considered promising while 15% or lower will not be considered as evidence of activity.

A Simon two-stage design with 90% targeted power and one-sided type I error of 5% will be employed for this study. With the assumption of 10% drop-out, the total sample size will be 32 patients to achieve 29 evaluable patients. During stage one, 13 evaluable patients will be enrolled. If there are 3 or more responses (CR+PR) observed, then the study will continue to the second stage of accrual, and 16 evaluable patients will be enrolled in the second stage. If there are 8 or more responses observed among 29 evaluable patients, the treatment will be considered promising.

With this design, the probability of terminating the study after 13 patients is 69% if the true response rate is 15%. The probability that the treatment will be considered promising is 5%, if the true response rate is 15%, and 90.7% if the true response rate is 40%. Allowing for a 10% unevaluability rate, the overall accrual goal will be 32 patients for the Phase II portion of this study.

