11.10. Interim Analysis

The Phase II portion of the study will follow a Simon two-stage design to compare a null ORR of 15% with an alternative ORR of 40% with 90% power and a one-sided type I error of 5%. The total sample size will be 29 evaluable patients. Thirteen patients will be enrolled in the first stage before triggering an interim analysis. At least three responses are required to proceed to the second stage. Eight responses among 29 patients are required for PLX3397 to be considered promising.

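### The stage 1 denominator is about 13 treated patients in the Synopsis and Section 5.1 but 13 evaluable patients in Section 11.1, and the stated operating characteristics belong only to the evaluable version

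*Combined protocol and SAP*

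**What the plan says.** The Synopsis (Study Design) and Section 5.1 carry the same rule: "an analysis of anti-tumor response will be carried out after approximately 13 patients have been treated". If at least 3 responses are seen, "an additional approximately 19 patients will be enrolled and treated". In both places responses may be judged by RECIST v1.1 or by PET imaging.

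Section 11.1, which holds the sample-size calculation, says "During stage one, 13 evaluable patients will be enrolled" and, after a positive interim, "16 evaluable patients will be enrolled in the second stage". The final rule is 8 or more responses among 29 evaluable patients. Total accrual is 32, to allow for 10% drop-out.

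The remaining descriptions do not decide between the two. Section 11.10 gives a total of 29 evaluable patients but then says "Thirteen patients will be enrolled in the first stage before triggering an interim analysis". The Synopsis (Statistical Considerations) and Sections 3.2 and 11.7 likewise say that thirteen are enrolled. Only Section 11.1 attaches the word evaluable to stage 1.

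**The concern.** Treated and evaluable are different counts in this protocol. Under Section 11.3 the efficacy population must meet the entry criteria and have a baseline CT, plus either an on-study CT or early progression or death before the first assessment. Section 11.1 expects 10% of patients to fall outside the evaluable set.

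The totals show where that allowance went. The design sections give 13 + 19 = 32; the statistics section gives 13 + 16 = 29. Read literally, the design sections place the whole 3-patient allowance in stage 2 and none in stage 1, while the cut-off of 3 responses stays the same.

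At stake is the go/no-go decision. If stage 1 closes at 13 treated and some are unevaluable, 3 responses are required from fewer informative patients, and an active drug may be stopped more often than the plan states.

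**Working it through.** **Inputs.** From Section 11.1:
- Response rates: "A true response rate of 40% or more will be considered promising while 15% or lower will not be considered as evidence of activity".
- Error rates: "A Simon two-stage design with 90% targeted power and one-sided type I error of 5% will be employed for this study".
- Stage 1 rule: "If there are 3 or more responses (CR+PR) observed, then the study will continue to the second stage of accrual".
- Final rule: at least 8 of 29 evaluable. Unevaluable rate: d = 10%.

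The treated version, 13 then 19, is from the Synopsis and Section 5.1.

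**Formulas.** With stage sizes n1 and n2 and true response rate p:
- P(stop at stage 1) = P(Bin(n1, p) ≤ 2)
- P(declared promising) = Σ over x ≥ 3 of P(Bin(n1, p) = x) × P(Bin(n2, p) ≥ 8 − x)

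**1. The plan's own figures (n1 = 13, n2 = 16, all evaluable).**
- p = 0.15: early stop 69.2%, type I error 5.0%.
- p = 0.40: early stop 0.0013 + 0.0113 + 0.0453 = 5.8%, power 90.7%.

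These match Section 11.1. The calculation is correct for the evaluable version.

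**2. Evaluable patients among 13 treated.** At 10% unevaluable the mean is 13 × 0.9 = 11.7. The chance that all 13 are evaluable is 0.9^13 = 25%.

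**3. Treated version at 10% unevaluable.** Assumptions: exactly 13 treated trigger the interim, RECIST responses only, no replacement. An unevaluable patient cannot supply a response, so the stage 1 response probability per treated patient is 0.40 × 0.9 = 0.36. Early stop is P(Bin(13, 0.36) ≤ 2) = 0.0030 + 0.0221 + 0.0746 = 10.0%.

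Power depends slightly on how stage 2 is run:

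| Convention | Power at 40% | Type I error at 15% |
|---|---|---|
| 13 + 19 treated, unevaluable counted as non-responders | 86.6% | 4.5% |
| Unevaluable excluded; 19 treated in stage 2, capped at 29 evaluable | 86.2% | 4.1% |
| Unevaluable excluded; stage 2 filled to 29 evaluable | 87.1% | 4.5% |

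With the stage 1 evaluable count fixed and 29 evaluable in total, 12 gives 88.6% and 11 gives 85.5%.

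**4. Sensitivity to the unevaluable rate (first convention).**

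| Unevaluable | Power at 40% | Type I error at 15% |
|---|---|---|
| 0% | 92.9% | 7.5% |
| 5% | 90.2% | 5.9% |
| 10% | 86.6% | 4.5% |
| 15% | 82.1% | 3.4% |
| 20% | 76.4% | 2.5% |

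Type I error exceeds 5% at the low rates because this convention applies the 8-response cut-off to all 32 treated rather than to 29 evaluable. Filling to 29 evaluable at 5% unevaluable gives 89.1% power and 4.8% type I error.

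**5. Sensitivity to the stage split (32 treated, 10% unevaluable, first convention).** 14 + 18 gives 88.9% power; 15 + 17 gives 90.4%, with type I error 5.1%.

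**The case against.** A reader might infer that the trial, as written, fails to deliver 90% power. The documents do not support that without conditions.

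- **Approximate counts.** The Synopsis and Section 5.1 say approximately 13 and approximately 19. Running 15 + 17 instead restores about 90% power (step 5), so the overview wording can accommodate the Section 11.1 design. It does not require it.
- **Replacement.** Section 8.4 lets patients withdrawn for reasons other than toxicity or clinically significant progression be replaced, and Section 7.6 says the same of noncompliant patients. Section 11.3 already counts early progression and death as evaluable. Replacement is discretionary, however, and no section ties it to the interim.
- **PET responses.** The rule in the Synopsis and Section 5.1 also counts PET responses, which can only raise the chance of passing stage 1. The documents give no PET-only response rate. Assuming 2%, 5% or 10% of evaluable patients respond on PET only, with PET counted at stage 1 alone and the first convention of step 3, early stopping at a 40% rate is 7.9%, 5.4% or 2.7%, and power is 88.1%, 89.9% or 91.7%. The 86.6% is thus the floor of that convention.
- **The 10% rate.** It is a whole-trial allowance, applied here to stage 1 in full. At 5% the loss largely disappears. At 10% the type I error falls below 5%, so the error there is conservative.
- **Section 11.10.** It might be read as a second treated rule. It says enrolled, alongside 29 evaluable in total, and is ambiguous rather than contradictory.
- **Discontinuation.** Section 5.1 records that the sponsor discontinued the study after 6 Pilot patients. No stage 1 decision is pending.

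These points make the size of the loss conditional and lower the urgency. They do not remove the two different denominators from the current text.

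**Conclusion.** The inconsistency is real: about 13 treated then about 19 in the Synopsis and Section 5.1, against 13 then 16 evaluable in Section 11.1, with the other sections silent on which is meant. The published operating characteristics are right for the evaluable version only.

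Under exactly 13 treated, RECIST responses alone, 10% unevaluable in stage 1 and no replacement, stopping at stage 1 when the response rate is 40% rises by about 4 points (5.8% to about 10%), and power falls by about 4 points (90.7% to about 86–87%), with type I error about 4.1–4.5%. At 5% unevaluable, power is about 90%, with type I error about 5.9% if the 8-response rule is applied to all 32 treated.

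This is a worthwhile correction, because a go/no-go rule needs one denominator. It is not critical, given the conditions and the discontinuation. Nor does the stated power need to be restated as 87%: aligning the wording makes the 90.7% hold.

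**What to change.** In the Synopsis (Study Design and Statistical Considerations) and Sections 3.2, 5.1, 11.7 and 11.10, state that the interim is triggered by the 13th evaluable patient and that stage 2 adds 16 further evaluable patients, within the planned total of 32. Use the evaluability definition in Section 11.3 throughout.

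At 10% unevaluable, 13 evaluable patients need 13 / 0.9 = 14.4, so about 14–15 treated before the interim. That leaves about 17–18 of the 32 for stage 2, in line with 16 / 0.9 = 17.8. The 69%, 5% and 90.7% then stand as written.

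The cost is a wording change and one or two more patients enrolled before the interim, with no change to the planned total.
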